Study Objective	The objective is to evaluate the effectiveness of the CapScan intestinal collection device in characterizing the regional distribution of sulfasalazine, the metabolic breakdown products of sulfasalazine, and the gut microbiota in the digestive tracts of healthy volunteers.		
Study Design	Prospective, open-label, single-arm study designed to provide effectiveness information on the CapScan intestinal collection device in healthy volunteers.		
Planned Sample Size	This study will be conducted in up to 10 healthy subjects.		

Inclusion	Subjects must meet all of the following criteria to be included in the study:
Criteria	Males or females 18 years of age or older and 70 years of age or younger at the time of the first Screening Visit.
	ASA Classification 1 or 2.
	For women of childbearing potential, negative urine pregnancy test within 7 days of Screening Visit and agreement to remain abstinent (refrain from heterosexual intercourse) or use adequate contraception during the treatment period and for 14 days after the final dose of sulfasalazine.
	Subject is fluent in English and understands the study protocol and informed consent and is willing and able to comply with study requirements and sign the informed consent form.

Exclusion	Subjects with any of the following conditions or characteristics must be		
Criteria	excluded from the study:		
	 Known or suspected gastrointestinal obstructions, strictures or fistul Known or suspected moderate to severe dysmotility, by the judgen of the principal investigator Gastroparesis A swallowing disorder Known intolerance, reaction or hypersensitivity to sulfasalazine, its metabolites, sulfonamides, or salicylates Urinary obstruction Porphyria G6PD deficiency Known or suspected infection with SARS-CoV2, HIV, HBV or HCV Pregnancy or planned pregnancy within 30 days from Screening Visi breast-feeding. Use of concomitant medications, such as aspirin, antibiotics, laxat and proton pump inhibitors that may interfere with the study in judgement of the investigator. Any form of active substance abuse or dependence (including dru 		
	 alcohol abuse), unstable medical or psychiatric disorder, or any chronic condition susceptible, in the opinion of the principal investigator, to interfere with the conduct of the study. A clinical condition that, in the judgment of the principal investigator, could potentially pose a health risk to the subject while involved in the study. 		
Device	The CapScan intestinal collection device is a single-use passive device that		
Description	collects fluids from the gastrointestinal ("GI") tract for analysis outside the body.		
	The CapScan Device contains no medicinal product. The CapScan Device is strictly a collection device.		
Study Treatment	At the Screening Visit, study eligibility is confirmed and the subject signs the informed consent document after all questions have been appropriately answered.		
	The subject is given 4 CapScan Devices and one 1,000 mg dose of sulfasalazine. The subject is provided with a snack bar to consume before swallowing the 4		

CapScan Devices. The subject is also given a retrieval wand and stool collection containers to snare the expelled CapScan Devices from the stool. The subject is also given 2 Tasso+ blood collection devices for home collection of blood samples, saliva and stool collection tubes for analysis of saliva and stool microbiome and metabolites. The blood, saliva and stool samples will be compared to the intestinal samples collected by the CapScan Device. The subject is given Daily Diaries to document the time the CapScan Devices were swallowed, what the subject ate, and time of bowel movements. On Day 1, the subject swallows 2 CapScan Devices and collects stool and saliva for the baseline set of measurements. On Day 2, the subject takes a single dose of 1,000 mg of sulfasalazine and swallows 2 CapScan Devices and collects 2 blood samples, plus stool and saliva. The timing of the dose of sulfasalazine, sampling of blood, and the ingestion of the CapScan Devices on each day will be at the discretion of the PI. The subject continues to collect all CapScan Devices expelled in the stool and stool samples until all ingested CapScan Devices have been retrieved, or until Day 8. In the event of missing CapScan Devices that were not successfully retrieved by the end of Day 8, and at the discretion of the PI, an abdominal xray will be performed on the subject to confirm no CapScan Devices are still in the body. In the event that a subject was unable to retrieve the 2 CapScan Devices swallowed on Day 2, or if the devices did not produce usable samples, the PI may request that the full set of procedures from Day 2 onwards will be repeated starting any day between Day 12-19 to give sufficient time for any sulfasalazine to be cleared from the body, including a second dose of 1,000 mg of sulfasalazine and swallowing and retrieval of the 2 additional CapScan Devices. The End of Study is defined when the last ingested CapScan Device is collected from the stool, or after determination by the PI that no CapScan Devices are in the subject's body. If a subject complains of any Adverse Event (AE) within 5 days of the End of Study that the investigator deems related to the device, the event will be documented and the subject will be evaluated by the principal investigator within 72 hours of the investigator becoming aware of the AE.

Endpoint	The endpoint of this trial is the regional measurement of sulfasalazine in the intestinal lumen, the metabolic breakdown products of sulfasalazine and the gut microbiota in the digestive tracts of healthy volunteers.
Safety Assessments	 Safety assessments will include the following: Subject-reported adverse events, as communicated to the study staff. A medical evaluation, if necessary, to evaluate an adverse event.
Statistical methods	All measured variables and derived parameters will be listed individually and, if appropriate, tabulated by descriptive statistics.

List of Abbreviations and Terms

Abbreviation/Term	Definitions
ADE	Adverse device effect
AE	Adverse event
ASA	American Society of Anesthesiologists
BMI	Body mass index
BSLN	Baseline
CE	Conformité Européenne
EC	Ethics committee
Cm	Centimeter
CRF	Case report form
CRO	Contract research organization
GCP	Good Clinical Practice
ICF	Informed consent form
ICH	International Conference for Harmonisation
ISO	International Standard Organization
Кg	Kilogram
Μ	Meter
MedDRA	Medical Dictionary for Regulatory Activities
Mm	Millimeter
μΙ	Microliter
Ν	Number of subjects
PI	Principal investigator
SADE	Serious adverse device effect
SAE	Serious adverse event
SAP	Statistical analysis plan
SEM	Standard error of the mean
WHO	World Health Organization
USP	United States Pharmacopoeia
RFID	Radiofrequency Identification Device

Table of Contents

1.	I	INTRODUCTION	13
	1.1	L CURRENT APPROACHES	13
2.	I	INVESTIGATIONAL DEVICE: CAPSCAN COLLECTION CAPSULE	14
	2.1	L DEVICE DESCRIPTION	14
	2.2	2 TREATMENT PROCEDURES	
	2.3	B DEVICE INTENDED USE	15
	2.4	RISK BENEFIT ANALYSIS	16
	2	2.4.1 Possible Risks	
	2	2.4.2 Possible Benefits	
	2	2.4.4 Safety Measures Taken	17
3.	S	STUDY RATIONALE	17
4.	S	STUDY OBJECTIVES	18
5.	s	STUDY DESIGN	18
6.	s	STUDY POPULATION	20
	6.3	3 SUBJECT IDENTIFICATION	21
	6.4	REMOVAL, REPLACEMENT, OR EARLY WITHDRAWAL OF SUBJECTS FROM THERAPY	OR ASSESSMENT
		21	
	6.5	6 HANDLING OF WITHDRAWALS	22
	6.6	5 SPONSOR'S TERMINATION OF STUDY	22
7.	s		
		STUDY PROCEDURES	22
	7.1		
	7.1 7.2	STUDY PROCEDURES CHART	
		STUDY PROCEDURES CHART	22 24
	7.2	STUDY PROCEDURES CHART SCREENING VISIT CAPSULE USE PHASE	22 24 25
	7.2 7.3	STUDY PROCEDURES CHART SCREENING VISIT CAPSULE USE PHASE PROTOCOL AMENDMENTS, REVISION AND/OR DEVIATIONS	
	7.2 7.3 7.3	 STUDY PROCEDURES CHART SCREENING VISIT CAPSULE USE PHASE PROTOCOL AMENDMENTS, REVISION AND/OR DEVIATIONS MANUFACTURING AND SUPPLY OF INVESTIGATIONAL DEVICE 	

APPENDIX A – DAILY DIARY

1. INTRODUCTION

It has recently been recognized that microbes, viruses, and micro-eukaryotes in the human gastrointestinal ("GI") tract perform many vital physiological functions that benefit their host organism, contributing to digestion, metabolizing drugs, producing essential amino acids and vitamins, regulating the immune system, providing resistance to disease, and even modifying appetite, and behavior.ⁱ Indeed it is estimated that the majority of drugs given orally today are metabolized or modified in some manner by the gut microbiome.ⁱⁱ Yet we know very little about the hundreds or thousands of microbial, viral, and micro-eukaryote species in the human GI tract ("microbiome").ⁱⁱⁱ The variety of microbes in a single individual at different regions of the GI tract is staggering. Due to the complexity of this microbial ecology in a single individual and the variability among individuals, it is necessary to routinely sample and analyze the microbial community living along with its associated metabolites in all regions of the GI tract and measure their interactions with orally-delivered drugs.

The CapScan intestinal collection device ("CapScan Device") is a non-invasive sampling device that collects gastrointestinal samples along the GI tract that are then analyzed outside the body. One specific utility for this type of sampling is that the CapScan Device may enable the characterization and the performance of various drugs by detecting the presence of the drug and its metabolic breakdown products in the digestive lumen. Samples collected by the CapScan Device will undergo DNA sequencing and metabolite analysis. The goal will be to determine the identity and function of sulfasalazine, the metabolic breakdown products of sulfasalazine, and the gut microbes in the different regions of the GI tract, for comparison to similar analyses conducted on concomitantly collected saliva, blood and stool samples.

The ability to combine information about the identities and diversity of microbial community members obtained from these measurements could provide an important understanding of the microbiome's role in human physiology. Furthermore, understanding how to better characterize metabolic breakdown of drugs within the digestive tract may potentially improve the development and optimization of oral or enterally administered treatments for various diseases.

1.1 CURRENT APPROACHES

STOOL SAMPLING

The least invasive way to assess the microbiome is analyzing stool samples. However, stool samples do not capture the microbial activity at proximal sites of the intestine or in microbes

living close to the gut mucosa.^{iv} Identification of microbes from stool reflects mainly the accumulated remnants of microbes that were more proximally active in the GI tract. Furthermore, many of the metabolites and proteins that are active in the small and large intestine are no longer present in the stool in their active form. Therefore, it is necessary to sample the microbiome directly from the stomach, small intestine and colon in order to accurately capture the full biochemical and immunological activity of the microbiome and its host interactions, and in order to better characterize the metabolic activity of drugs.

ENDOSCOPIC BIOPSIES

Endoscopic mucosal biopsies display greater microbial diversity than stool samples.^v However, mucosal biopsies are associated with the invasiveness and risk of endoscopy, as well as the biopsy procedure that alters the mucosal surface of the GI tract.

To the best of our knowledge, no device exists to safely, routinely and non-invasively collect fluid samples from the various regions of the GI tract to provide highly relevant samples for microbiome and pharmocological function analysis.

BLOOD SAMPLES

Blood samples show how much of the drug is in systemic circulation. However, for drugs such as sulfasalazine that work in the gut lumen, circulating levels of the drug in blood may not be informative.

2. INVESTIGATIONAL DEVICE: CAPSCAN COLLECTION DEVICE

2.1 DEVICE DESCRIPTION

The CapScan Device is a single-use passive device that collects fluids from the gastrointestinal ("GI") tract for analysis outside the body.

The CapScan Device contains no medicinal product. The CapScan Device is strictly a collection device.

2.2 TREATMENT PROCEDURES

The subject is given 4 CapScan Devices and one 1,000 mg dose of sulfasalazine. The subject is provided with snack bars to consume before swallowing the CapScan Devices. The subject is given a retrieval wand to snare the expelled CapScan Devices from the toilet bowl and stool collection containers if they prefer to retrieve the device from stool in the container as opposed to from the toilet. The subject is also given 2 Tasso+ home-use blood collection devices, saliva

and stool collection tubes for analysis of blood, saliva and stool microbiome and metabolites. The blood, saliva and stool samples will be compared to the intestinal samples collected by the CapScan Device. The subject is given Daily Diaries to document the time the CapScan Devices were swallowed, blood and saliva samples collected, what the subject ate, and time of bowel movements.

On Day 1, after consuming a snack bar, the subject swallows 2 CapScan Devices and collects stool and saliva for the baseline set of measurements.

On Day 2, after consuming a snack bar, the subject takes a single dose of 1,000 mg of sulfasalazine and swallows 2 CapScan Devices and collects blood, stool and saliva.

The timing of the dose of sulfasalazine, sampling of blood, stool and saliva and the ingestion of the CapScan Devices on each day will be at the discretion of the PI.

The subject continues to collect all CapScan Devices expelled in the stool until all ingested CapScan Devices have been retrieved, or until Day 8. In the event of missing CapScan Devices that weren't successfully retrieved by the end of Day 8, and at the discretion of the PI, an abdominal x-ray will be performed on the subject to confirm no CapScan Devices are still in the body.

In the event that a subject was unable to retrieve the two CapScan Devices swallowed on Day 2 or if the devices did not produce usable samples, the PI may request that the full set of procedures from Day 2 will be repeated on one day between Day 12-19 to give sufficient time for any sulfasalazine to be cleared from the body, including a second dose of 1,000 mg of sulfasalazine and swallowing and retrieval of 2 additional CapScan Devices. The End of Study is defined when the last ingested CapScan Device is collected from the stool, or after determination by the PI that no CapScan Devices are in the subject's body.

If a subject complains of any Adverse Event (AE) within 5 days of the End of Study that the investigator deems related to the device, the event will be documented and the subject will be evaluated by the principal investigator or sub investigator within 72 hours of either investigator becoming aware of the AE.

2.3 DEVICE INTENDED USE

The CapScan Device is intended to collect liquid samples from the small intestine and colon.

2.4 RISK BENEFIT ANALYSIS

2.4.1 Possible Risks

The potential risks associated with the use of CapScan Device include transient discomfort when swallowing a CapScan Device. Additional risks include aspiration and intestinal blockage.

The risks above are considered reasonable given the following safeguards:

Physically, the size and shape of the CapScan Device is similar to a standard size 00 medicinal capsule. As such, the swallowing of the CapScan Device does not pose any greater risk to the health, safety, or welfare of the patient than the swallowing of a standard medicinal capsule.

The passage of the CapScan Device through the GI tract does not present any greater risk to the health, safety, or welfare of the patient than a Medtronic Pillcam[®], which is routinely swallowed for diagnostic purposes and eliminated via defecation. The Pillcam[®] is hard and inflexible and is 12 mm in diameter, *versus* the CapScan Device which is soft and flexible and only 6 mm in diameter. A radio-opaque marker incorporated into the CapScan Device enables definitive confirmation that the device has been eliminated from the body, if necessary.

Generally, healthy volunteers with any underlying intestinal stricture that would prevent the passage of items 6 mm in diameter through the GI tract would be symptomatic even before the study. Examples of symptoms of pre-existing intestinal blockage could include pain and bloating after eating corn or other vegetables, for example.

In the unexpected event that the CapScan Device is retained in the intestines, the CapScan Device can be removed via motility enhancers (i.e. laxatives) or via laparoscopic surgery in a worst case scenario. In the event of a retained CapScan Device, there is a potential benefit for the subject to discover and treat the underlying cause of any pre-existing intestinal strictures inadvertently discovered as part of this study.

All of the materials in the CapScan Device have been well characterized and understood to be biocompatible and used in a variety of cleared medical products and pharmaceuticals.

Sulfasalazine is an FDA-approved drug indicated for treatment of ulcerative colitis and rheumatoid arthitis. In clinical practice, sulfasalazine is most commonly associated with the following side effects: gastric distress, headache, nausea, oligospermia (temporary reduced sperm count), vomiting, and anorexia. Less frequent side effects include pruritis (itching), urticaria (hives), rash, fever, Heinz body anemia, hemolytic anemia, and cyanosis.

Research and clinical experience suggests that side effects are more frequent in individuals taking daily doses of 4,000 mg or higher and for prolonged periods of time (months to years). Due to the relatively low single dose of 1,000 mg sulfasalazine administered in this study, side effects are expected to be rare and less serious. Regardless, subjects will be instructed to report any experienced side effects to the study investigator.

Finally, the proposed clinical investigation does not involve any anticipated surgical procedures, nor do any of the other clinical procedures proposed for use during the study present a potential for serious risk to the health, safety, or welfare of a subject.

2.4.2 Possible Benefits

The possible benefits offered by the CapScan Device for future patients might be the development of better predictive models on the effectiveness of sulfasalazine and/or other drug therapies, disease diagnosis, patient stratification, and potentially the development of transformative treatments for various diseases.

2.4.3 Alternative Treatments Summary

Alternative approaches for collecting samples from the GI tract and looking for drug pharmacokinetics, include measuring the drug levels in the blood and/or stool samples, which are not representative of the actual luminal drug levels or and only offer limited insight into effects of the gut microbiome on drug metabolism.

2.4.4 Safety Measures Taken

Physically, the size and shape of the CapScan Device is similar to a standard size 00 medicinal capsule. As such, the swallowing of the CapScan Device does not present any greater risk to the health, safety, or welfare of the patient than the swallowing of a standard medicinal capsule.

The passage of the CapScan Device through the GI tract does not present any greater risk to the health, safety, or welfare of the patient than a Given Imaging Pillcam[®], which is routinely swallowed and eliminated via defecation and is significantly harder, larger and more voluminous than the CapScan Device. The radio-opaque marker incorporated into the CapScan Device enables definitive confirmation that the device has been eliminated from the body if necessary.

All of the materials in the CapScan Device are well characterized and understood to be biocompatible and used in a variety of cleared medical products and pharmaceuticals.

The considerations mentioned above have been taken during the design and manufacturing of the CapScan Device to ensure its safe and reliable performance.

The selection of and dosage of sulfasalazine is intended to minimize observed side effects related to the drug used for metabolic analysis.

3. STUDY RATIONALE

Performing drug metabolism and microbiome analyses on stool samples does not fully represent the diversity of the microbial, viral and micro-eukaryotic species, metabolism and host interactions occurring in the intestines. Obtaining samples via endoscopic biopsy is invasive and not convenient. Understanding drug levels in the lumen of the gut will provide insight into drug metabolism and pharmacokinetics as well as enable an understanding of systemic versus intestinal lumen drug concentrations.

The CapScan Device is designed to be a safe and convenient method for obtaining gastrointestinal samples from key regions of the GI tract for microbiome analysis. This study is focused on examining the safety and efficiency of sample collection of the CapScan Device in humans, as well as its suitability for adequate sample collection process aimed at subsequent DNA, metabolite and drug pharmacokinetics and metabolism analyses. Sulfasalazine was selected as the drug for metabolic characterization based on its safety profile and low likelihood of causing harm to healthy subjects when ingested for analytical purposes. Furthermore, sulfasalazine is degraded by gut microbes into known metabolites, although to the best of our knowledge, this process has not been observed directly in the human gut before.

The trial sample size is considered the minimal size required to collect sample collection efficiency data.

4. STUDY OBJECTIVES

The objective is to evaluate the effectiveness of the CapScan Device for characterizing the regional distribution of sulfasalazine, the metabolic breakdown products of sulfasalazine and the gut microbiota in the digestive tracts of healthy volunteers.

5. STUDY DESIGN

This will be an open-label feasibility study conducted in up to 10 subjects at a single center.

All subjects will undergo similar pre-study screening and evaluation and study procedures.

SCREENING VISIT:

During the Screening Visit, study eligibility is confirmed, the informed consent process is properly conducted and documented and instructions are given for use of the CapScan Device, saliva and stool collection, ingestion of sulfasalazine, and completion of the Daily Diaries.

The CapScan Devices are provided in individually-sealed containers.

DAY 1:

2 CapScan Devices are swallowed on Day 1. The subject will eat a study-provided snack bar and swallow the CapScan Devices at times of the day that are at the discretion of the PI. The subject also collects saliva and stool samples using the collection kits provided to them.

The subject uses a retrieval wand to snare any CapScan Devices that are expelled together with the stool.

The retrieved CapScan Devices, saliva and stool samples are stored in closed containers inside a study-supplied refrigerator until collected by the study staff.

The subject will complete a daily diary to document the time the CapScan Devices were swallowed, what they ate, when they sampled saliva, when they had bowel movements and the time the CapScan Devices were recovered, if any were recovered.

DAY 2:

Two CapScan Devices are swallowed on Day 2. The subject will also eat a study-provided snack bar and take the physician-directed dose of 1,000 mg of sulfasalazine. The subject also collects up to two samples of blood using the Tasso+ device, saliva and stool samples using the collection kits provided to them. The timing of the above procedures will be at the discretion of the PI.

The subject will retrieve the CapScan Devices from the stool using the retrieval wand provided by the study sponsor.

The subject will complete a daily diary to document the time the CapScan Devices were swallowed, what they ate, when they swallowed the sulfasalazine, sampled blood and saliva, had bowel movements and the time the CapScan Devices were recovered, if any were recovered.

DAYS 3-8:

The subject will continue to retrieve the CapScan Devices, collect stool and complete the daily diaries until the last device is retrieved. If not all devices have been retrieved by Day 8, the PI may elect to perform an abdominal x-ray to confirm that no CapScan Devices are still in the body. The End of Study is defined when the last ingested CapScan Device is collected from the stool, or after determination by the PI that no CapScan Devices are in the subject's body.

DAYS 12-19, if needed:

In the event that a subject was unable to retrieve the two CapScan Devices swallowed on Day 2 or if the devices did not produce usable samples, the PI may request that the full set of procedures from Day 2-8 will be repeated starting on any day between Day 12-19 to give sufficient time for any sulfasalazine to be cleared from the body, including a second dose of 1,000 mg of sulfasalazine and swallowing and retrieval of 2 additional CapScan Devices. The end of the study is defined when the last swallowed CapScan Device is retrieved from the stool or after determination by the PI that no CapScan Devices are in the subject's body. At this point, a study representative will go to the subject's house to collect all unused CapScan Devices,

retrieved devices, blood, saliva and stool samples, refrigerator and the Daily Diaries from the subject.

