7.3 CAPSCAN DEVICE USE PHASE

- The CapScan Devices are provided in a sealed containers.
- The subject uses a device retrieval wand to look for and collect the expelled devices in the stool after all bowel movements for up to 8 days after swallowing a CapScan Device.
- The end of the study is defined when the last swallowed CapScan Device is retrieved from the stool. The study representative will collect all of the retrieved samples and the Daily Diaries from home of the subject.

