8. STUDY ASSESSMENT METHODS

8.1 SAFETY ASSESSMENTS

8.1.1 Adverse Events

Adverse Events (AE's) reported by subjects or observed by the PI or PI designee will be documented in the source document, assessed by the PI and will be individually listed on an adverse event page in the CRF. Recording of AE's will begin immediately after the signing of the informed consent document and continue until the subject dies, withdraws consent, or 48 hours after the End of Study (EOS), regardless of the relationship of the AE to the CapScan Device. If a subject complains of any AE within 5 days of the EOS that the PI deems definitely, probably, or possibly related to the device, the event will be documented and followed until all parameters

(including laboratory) have returned to normal, stabilized, or are otherwise explained. The subject will be evaluated by the PI within 72 hours of the PI becoming aware of the AE.

Information to be collected includes type of event, date of onset, date of resolution, investigator-specified assessment of severity and relationship to device, seriousness, as well as any action taken.

All conditions present before the Screening Visit will be documented as medical history.

Specific procedures for recording and reporting serious adverse events are described in section 10.5.

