10.5 REPORTING OF ADVERSE EVENTS

Any Serious adverse event (SAE) and device respectively procedure-related (Relatedness: definite, probably and possibly) Adverse Effect (SADE), must be fully recorded utilizing the sponsor provided SAE form and reported in writing by the Principal Investigator to Envivo Bio Inc. within 24 hours of becoming aware of the event.

The PI will complete the Serious Adverse Event Form and email a scanned copy to Envivo Bio Inc. sponsor and the medical monitor contacts as follows:

Additional information (follow-up) about any SAE or SADE unavailable at the initial reporting should be forwarded by the site to the Envivo Bio Inc. as soon as they become available (such as hospital discharge).

Envivo Bio Inc. will review and assess with the PI any SAE's and any serious device/procedurerelated adverse effects. Envivo Bio Inc. ensures that reporting requirements according to the local regulations are fulfilled.

All SAE's which are considered as device- or procedure-related will be reported to IRB by the PI.

Subjects who have had an SAE during the Treatment Phase must be followed clinically until all parameters (including laboratory) have returned to normal, have stabilized, or are otherwise explained. The study period for the purpose of SAE reporting is defined as the period from time of informed consent until 14 days after the End of Study.

If the investigator detects a SAE in a trial subject after the end of the period of observation, and considers the event possibly related to the prior trial, he should contact the sponsor to determine how the AE should be documented and reported.

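### All-cause adverse event recording can close 2 to 14 days before a permitted repeat round, because retrieving the first-round devices already meets End of Study; follow-up after the dose also varies with device transit

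*Combined protocol and SAP*

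**What the plan says.** **End of Study.** Section 5 (Days 3-8) gives two routes: "The End of Study is defined when the last ingested CapScan Device is collected from the stool", or the investigator determines that no device is in the body. The Synopsis (Study Treatment) and Section 2.2 agree. Section 5 (Days 12-19) restates the rule after describing a repeat: "The end of the study is defined when the last swallowed CapScan Device is retrieved from the stool or after determination by the PI" to the same effect. Section 7.3 (CapScan Device Use Phase) has the first route only: "The end of the study is defined when the last swallowed CapScan Device is retrieved from the stool".

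**Repeat round.** Section 5 allows one if the Day 2 devices were not retrieved, "or if the devices did not produce usable samples, the PI may request that the full set of procedures" from Day 2-8 again, starting on any day from Day 12 to Day 19 and including a second dose.

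**Safety windows.** All are counted from End of Study.
- All-cause AEs (Section 8.1.1): recorded from consent until death, withdrawal of consent, "or 48 hours after the End of Study (EOS), regardless of the relationship of the AE to the CapScan Device".
- Complaints within 5 days of End of Study (Section 8.1.1): documented if judged related to the device.
- SAEs (Section 10.5): "from time of informed consent until 14 days after the End of Study".

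**Schedule and analysis.** Table 1 (Section 7.1) shows AE/SAE collection during device use and during retrieval of up to 8 days, with no column for a repeat. Section 11 summarises AE incidence over a treatment period that it does not define.

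**The concern.** The unusable-sample trigger presupposes that devices were retrieved, and retrieval of the last one is the event that meets End of Study. When the last device out is one of the Day 2 pair, its contents cannot be judged before that moment. The AE clock may therefore have started, and run out, before anyone knows that a repeat is needed. No section makes End of Study wait for the repeat decision or tells the site to keep recording meanwhile.

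After 48 hours, the 5-day extension takes only device-related complaints. A non-serious event attributed to sulfasalazine, or to nothing in the study, then has no recording rule until a repeat begins.

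Tying the window to device exit also gives subjects different observation times after the same dose, and Section 11 pools them in one incidence. Section 12 names safety among the things the study is to demonstrate. With 10 subjects, missing the only event in one subject moves an incidence by 1/10, or 10 percentage points.

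**Working it through.** The plan gives no figure of its own to reproduce here. The check is whole-day arithmetic on the stated windows.

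**Inputs**
- First dose and second device pair: Day 2 (Section 5).
- First-round End of Study, day *e*: 3 to 8. Day 8 is the first-round limit in Section 5; the range is an assumption because the documents give no transit times.
- Repeat start, day *r*: 12 to 19 (Section 5).
- Window closes: all-cause AE at *e* + 2, device-related AE at *e* + 5 (Section 8.1.1), SAE at *e* + 14 (Section 10.5).

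**Gap before a repeat** = *r* − (*e* + 2)

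| End of Study | All-cause AE closes | Gap to Day 12 | Gap to Day 19 | Device-related closes | SAE closes |
|---|---|---|---|---|---|
| Day 3 | Day 5 | 7 days | 14 days | Day 8 | Day 17 |
| Day 5 | Day 7 | 5 days | 12 days | Day 10 | Day 19 |
| Day 8 | Day 10 | 2 days | 9 days | Day 13 | Day 22 |

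**All combinations.** There are 6 End of Study days × 8 repeat days = 48.
- All-cause AE window closes before the repeat: 48 of 48.
- Device-related window closes before the repeat: 45 of 48. The exceptions are End of Study Day 7 with repeat Day 12, and Day 8 with repeat Day 12 or 13.
- SAE window closes before the repeat: 3 of 48. These are End of Study Day 3 with repeat Day 18 or 19, and Day 4 with repeat Day 19.

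These are counts of calendar combinations, not probabilities.

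**Sensitivity.** For the all-cause window to reach the repeat, End of Study must fall on Day 12 − 2 = Day 10 or later for a Day 12 repeat, and on Day 19 − 2 = Day 17 or later for a Day 19 repeat. Section 7.3 has the subject look for devices for up to 8 days after swallowing, which is Day 2 + 8 = Day 10 for the second pair, against Day 8 in Section 5. On the Day 10 limit, recording closes on Day 12: no gap to a Day 12 repeat and 7 days to a Day 19 repeat. If Day 2 devices are never found, End of Study rests on an investigator determination with no deadline. Made on Day 8 or 9, it closes recording on Day 10 or 11; made later, the gap shrinks or disappears.

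**Follow-up after the Day 2 dose, no repeat** = (*e* + 2) − 2 = *e* days. That is 3 days for End of Study on Day 3 and 8 days for Day 8.

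**The case against.** The best defence is that Section 8.1.1 describes one continuous run from consent to 48 hours after a single End of Study. For a subject who repeats, the last ingested device is a repeat device, and the Days 12-19 paragraph restates the end of study there. On that reading there is no gap. The reading is available, so recording *can* close early rather than *must*. It does not settle the matter: the Days 3-8 definition is already met when the first-round devices are out, and the site cannot know then that a later decision will move the date.

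Some stronger inferences are tempting but not supported.
- *Events after the second dose go unrecorded.* A repeat covers the whole set of Day 2-8 procedures, and Table 1 includes AE/SAE collection in both phases. Recording restarts with the repeat; the exposed period ends there.
- *SAE reporting generally lapses before the repeat.* It does so in only 3 of 48 combinations. Section 10.5 also sends a possibly related SAE detected after the observation period to the sponsor.
- *A device lost in the toilet means End of Study never occurs.* Only Section 7.3 read alone says so. The Synopsis, Section 2.2 and Section 5 all give the investigator-determination route, so this is an inconsistency between sections.

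It is also fair that no section dates the usability check and that earlier pick-up of samples is not excluded. That usability is judged after End of Study is therefore partly inference, though firm for a Day 2 device that is the last to be recovered. Finally, the analysis is descriptive and single-arm, AEs are listed with onset, and the diary has a field for dose time, so time since dose can be recovered for recorded events. It cannot be recovered for events that were never recorded.

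**Conclusion.** The point holds as a gap in the interval before a repeat, not after it. With first-round End of Study on Day 3-8, all-cause recording can close on Day 5-10, leaving 2-14 days uncovered before a repeat on Days 12-19. Mainly non-serious events are affected, above all those not attributed to the device. The size rests on the assumed Day 3-8 range and on a site applying the first End of Study definition when it is met.

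Two related points stand apart from any repeat: all-cause follow-up after the Day 2 dose ranges from 3 to 8 days according to device transit, and Section 7.3 disagrees with the Synopsis, Section 2.2 and Section 5 on how the study can end. This should be corrected. It changes which safety data are collected, and the repair is mostly wording.

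**What to change.** 1. **One End of Study definition** in the Synopsis, Section 2.2, both places in Section 5, and Section 7.3. It is met when all devices from all rounds are retrieved, or determined by the investigator not to be in the body, **and** either the repeat is complete or a decision not to repeat has been recorded. Give that decision a stated deadline no later than Day 19, the end of the repeat window.
2. **Continuous AE recording** in Section 8.1.1: from consent, through any interval before a repeat, to the later of 48 hours after that End of Study and a fixed number of days after the last dose. The sponsor sets the number, the same for all subjects. The 48-hour rule alone would still leave follow-up dependent on transit.
3. **Analysis** in Section 11: replace the undefined treatment period by that common period after each dose, and summarise AE incidence over it. If the period exceeds 10 days (Day 12 − Day 2), the period after the first dose can run past the earliest repeat, so say how events there are assigned.
4. **Reconcile** Table 1 (Section 7.1) and Sections 8.1.1, 10.5 and 11 with the new definition, and the two device-retrieval limits in Sections 5 and 7.3 with each other.

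The cost is wording in these sections and some extra days of recording. For a subject who does not repeat, a decision as late as Day 19 would close the 48-hour window on Day 19 + 2 = Day 21, against Day 5-10 now. That is at most 11-16 extra days from the decision rule, and fewer with an earlier deadline; the fixed period after the last dose could add to this.
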